Mean Predicted	5.00	4.50	4.33	4.00	2.00	4.80	2.00	5.00	5.50
SD	2.20	0.71	0.58	0.00	1.00	1.10	0.00	1.15	2.00
Range	1.00	4.00	4.00	0.00	1.00	5.00	0.00	5.50	4.00

S ur ge ry Le ng th (H ou rs)	C o m bi ne d M ea n Pr ed ict ed S ur ge ry Le ng th (H ou rs)	0 . 9 5
	4.14 ± 1.41	4.03 ± 1.53

Statistical Analysis

Sample size determination

There was a predicted sample difference of 20% in terms of muscular activity between the RS and LS groups based on previously conducted research (Epstein *et al.*, 2018). Sample size was calculated in R Studio using the 'pwr' package and the 'pwr.f2.test' function. With a maximum of ten predictor variables, a large effect size (Cohen's $d=0.8$), $\alpha=0.05$, and a desired statistical power of 0.90, this resulted in a sample size of 30 (RALS $n=15$, LS $n=15$). This was calculated for the right-sided muscle activation in RS compared to LS.

Statistical Analysis

All analyses were conducted using Jamovi version 2.3.21. Data is presented in text and tables as means and standard deviations (SD) unless otherwise stated. Alpha level is reported as exact p values and not described dichotomously as 'significant' or otherwise as recommended by the American Statistical Association (Hurlbert *et al.*, 2019). Effect sizes for the linear mixed effects models are reported using conditional and marginal R^2 when considering the overall model fit. Cohen's D is used for specific pairwise comparisons (Lakens., 2013).

Analysis of participant characteristics of Table 1. was conducted using student's t-test. When comparing age, body mass, height, glove size and years of experience between groups, this data was found to be normally distributed. A Mann-Whitney U test was used to analyse the difference between the groups' BMI and estimated expenditure of METs/ week as thesis data were not normally distributed. When comparing the mean surgery length for RALS and LS procedures a Mann-Whitney U test was conducted as data violated normality of distribution.

The normality of distribution of the EMG %MVC_{RMS} data was examined using a Shapiro-Wilk test. Data was not normally distributed so a linear mixed-effects model was conducted with a subsequent restricted maximum likelihood (REML) estimation and Type III fixed-effects tests. The linear mixed-effects model was conducted with surgery type (RALS vs LS), side of the body (left vs right), time (30, 60, 90 and 120 minutes) and muscle group (sternocleidomastoid vs forearm) as fixed effects and surgeon code as a random effect. This was then used to examine the differences in muscle activation in RS and LS when comparing the sampled time points.

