Surgeons that took part in this study must have obtained a Certificate of Completion of Training (CCT). This allowed for confidence that they were proficient in performing surgical practice.

Exclusion Criteria

Procedures with major complications (above 50% more time than the average for that surgery).

Surgeon suffering from significant co-morbidities (such as heart disease or other advanced chronic conditions) that could affect the results of the study due to this obstructing normal surgical performance.

Surgeons suffering from significant musculoskeletal injury or disorder that may cause the surgeon to deviate from their normal practice or obstruct optimal performance.

Anything the investigator feels will affect the quality of the data obtained or the safety of experimentation/those involved.

Group characteristics

Altogether, 9 surgeons participated in this study, with 1 surgeon participating in both groups, meaning that the RALS group consisted of n=3 and LS group consisted of n=7 with specialties of colorectal, general and hepatobiliary surgery. Subject demographics are presented in the table below.

Table 1. Surgeon demographics for both groups. Data shown as mean \pm SD.

	RALS (n=3)	LS (n=7)	p Values
Age (Years)	48 \pm 7	47 \pm 7	0.724
Body Mass (kg)	84.7 \pm 10	79.5 \pm 13.9	0.589
Height (cm)	176 \pm 7.64	172 \pm 6.77	0.379
BMI (kg/m²)	27.2 \pm 1.07	26.8 \pm 10.4	0.732
Handedness (Left, Right)	1,2	0,7	n/a
Average Glove Size	7.76 \pm 0.289	7.07 \pm 0.838	0.277
Muscle Pain In the Last Year	Shoulder	1	3
	Neck	1	3
	Wrists/ Hands	None	1
	Upper Back	None	2
Estimated METs / Week (ml/kg/min)	7800 \pm 5234	3445 \pm 4418	0.137
General Health	Excellent	1	1
	Very Good	None	4
	Good	1	1
	Fair	1	None
Years of Experience	5.3 \pm 2.52	17.9 \pm 6.82	0.017

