To assess the reliability of EMG, the coefficient of variation (CV) was calculated for each muscle group bilaterally, providing insight into the inter-test reliability. This was calculated both at rest and during an MVC. A lower CV means greater reliability and acceptable results were based on similar research in the field (Brown, 1998). The sternocleidomastoid EMG CV at rest was 8.1% and 7.9% for the right and left side, respectively. The forearm EMG CV at rest was 6.9% and 8.2% for the left and right, respectively. When tested during MVC the sternocleidomastoid showed average variations of 18.3% for the right and 16.1% for the left and the CV data for the forearms showed 15.9% for the right and 19.2% for the left. All data was within the commonly acceptable level of variability (Fauth *et al.*, 2020; Norcross *et al.*, 2010; Balshaw *et al.*, 2017; Trentzsch *et al.*, 2023).

The surgeon then performed their isometric MVC of both muscle groups bilaterally before beginning the surgery and data were recorded. Data were collected for 120 s at four 30-minute intervals. The EMG data was collected at a sampling frequency of 2000 Hz. This was filtered through a high-pass (10 Hz) and low-pass (500 Hz) filter. After this stage the raw data was smoothed using root mean squared (RMS) (EMG Works, Delsys Inc., Boston, MA). The final step was averaging out the RMS EMG from each collection period to be normalized to the previously collected MVC EMG and quantified as %MVC_{RMS}.

Surgical Procedures

With the aim of enabling comparison between surgical procedures, data were collected within 2-minute collection windows at four points during the surgery: 30 minutes, 60 minutes, 90 minutes and finally 120 minutes. This was done to reduce the effect of surgery duration. All laparoscopic procedures, including robotic procedures, begin with the surgeons creating trocars (laparoscopic ports in the abdomen) so the beginning of the timing of the surgery began when the first incision was made to create the first trocar as is standard procedure. If the surgeon took a break during the

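### The sample size quotes Cohen's d = 0.8 for a function that takes f²; at d = 0.8, 30 operations give about 0.56 power for RALS versus LS, not 0.90

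*Protocol*

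**What the plan says.** Under Sample size determination the protocol starts from a predicted 20% difference in muscle activity. It reports that the calculation was done "using the 'pwr' package and the 'pwr.f2.test' function". The inputs are given as "With a maximum of ten predictor variables, a large effect size (Cohen's $d=0.8"), alpha 0.05 and power 0.90, with the result "and a desired statistical power of 0.90, this resulted in a sample size of 30 (RALS $n=15$, LS $n=15"). The target is then narrowed to a single comparison: "This was calculated for the right-sided muscle activation in RS compared to LS".

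The section gives no f², no numerator or denominator degrees of freedom, no SD behind the 20%, and no unit for the 30. The unit can be inferred. Group characteristics reports that "Altogether, 9 surgeons participated in this study, with 1 surgeon participating in both groups", while the cases under Distribution of Procedures add up to 14 RALS (4 + 1 + 2 + 3 + 3 + 1) and 16 LS (5 + 3 + 4 + 1 + 1 + 1 + 1). The 30 must therefore be operations.

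**The concern.** The function named and the effect size named are on different scales. pwr.f2.test has no argument for d, so a d of 0.8 must be converted before it is used, and no conversion is reported. If 0.8 was entered unconverted, the calculation was for a much larger effect than the one printed.

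This paragraph is the only justification given for 30 operations. A reader who accepts 0.90 power at d = 0.8 would take an inconclusive RALS–LS comparison as fairly strong evidence against an effect of that size. If the true power is near 0.56, such an effect would be missed about 44% of the time (1 − 0.56).

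**Working it through.** **Inputs** (Protocol, Sample size determination): d = 0.8, at most 10 predictors, alpha 0.05 (taken as two-sided), power 0.90, N = 30 split 15/15.

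**Formulas**
- Conversion for two equal groups: f² = d²/4 = 0.64/4 = 0.16. In reverse, f² = 0.8 corresponds to d = 2√0.8 = 1.79.
- pwr.f2.test: power = P(F′ > F crit), where F′ is noncentral F with u and v degrees of freedom and noncentrality λ = f²(u + v + 1).
- With ten predictors in the model, N = v + 11, so N = 30 means v = 19.
- Two-sample t test: noncentrality d/√(1/n₁ + 1/n₂) on n₁ + n₂ − 2 degrees of freedom.

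**Step 1: trying to reproduce 30, ten predictors tested jointly (u = 10)**

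| f² | v for 0.90 | N needed | Power at N = 30 |
|---|---|---|---|
| 0.8 (0.8 entered unconverted) | 24.96 | 36 | 0.78 |
| 0.16 (d = 0.8 converted) | 126.75 | 138 | 0.18 |

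Here 0.90 at N = 30 needs f² = 1.06. Neither reading gives 30.

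**Step 2: one contrast in a ten-predictor model (u = 1, v = 19)**

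| f² | N needed for 0.90 | Power at N = 30 |
|---|---|---|
| 0.8 | 25 | 0.97 |
| 0.64 (d² not divided by 4) | 28 | 0.94 |
| 0.16 | 77 | 0.41 |

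Here 0.90 at N = 30 needs f² = 0.56, about 3.5 times 0.16. The 0.41 is what the function itself returns: it sets λ = 0.16 × (1 + 19 + 1) = 3.36, which counts 21 observations rather than 30. With λ = 0.16 × 30 = 4.8 and v = 19, power is 0.55.

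**Step 3: the plain contrast at d = 0.8**
- 15 versus 15: noncentrality 0.8/√(2/15) = 2.19 on 28 df, power 0.56.
- 14 versus 16, as in the case list: power 0.56.
- One-sided, 15 versus 15: power 0.69.
- For 0.90, two-sided: 34 per group, 68 in all.
- Effect detectable with 0.90 power at 15 versus 15: d = 1.23, that is f² = 1.226²/4 = 0.38, about 2.3 times 0.16.

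**Step 4: could repeated readings close the gap?** The Electromyography section says "Data were collected for 120 s at four 30-minute intervals". Suppose d refers to the SD of a single reading and four equally correlated readings are averaged. The effective d is then 0.8/√((1 + 3ρ)/4). The correlation ρ is not in the protocol, so these values are assumptions:

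| ρ | Effective d | Power, 15 vs 15 |
|---|---|---|
| 0.9 | 0.83 | 0.59 |
| 0.5 | 1.01 | 0.76 |
| 0.2 | 1.26 | 0.92 |

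**Step 5: clustering, for direction only.** There are 3 RALS and 7 LS surgeons, so about 30/10 = 3 operations per surgeon and group. With an assumed intraclass correlation of 0.1 to 0.5, the design effect 1 + 2 × ICC is 1.2 to 2.0, and 30 operations carry the information of about 25 to 15.

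**The case against.** The strongest reply is that the call is not shown and may have been internally valid. One contrast in a ten-predictor model with f² = 0.64 or 0.8 needs only 28 or 25 operations, and other settings land near 30 too: u = 4 with f² = 0.64 gives exactly 30, and u = 1 with f² = 0.4 gives 29. The fault would then be a mislabelled effect size. This stands as a reason to ask for the inputs first. It does not rescue the text, because each of these calls uses an f² at least 2.5 times the 0.16 that d = 0.8 implies.

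A second reply is that each operation yields several readings. Averaging four passes 0.90 when ρ is below about 0.23. If both muscle groups on the right side are also averaged, eight readings give 0.92 at ρ = 0.3 and 0.81 at ρ = 0.5. This stands as a condition on the 0.56, which assumes one value per operation. It depends, however, on a per-reading d and a low correlation that the protocol never states, and surgeon clustering pulls the other way.

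A third reply is that 0.41 understates power at N = 30, since it comes from the function's noncentrality convention. That is fair: 0.55 to 0.56 is the better description of the design, and 0.41 is only what the named function would print.

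Finally, the operations are already done, so no estimate or p value changes. That is true, but the power claim still governs how an inconclusive result is read.

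**Conclusion.** The concern holds. The effect size is quoted on a scale that the named function does not accept, and the stated d, power and N do not fit together. At d = 0.8, the RALS–LS contrast with 30 operations has power of about 0.56 (0.55 with ten predictors in the model) against a stated 0.90. To keep 0.90, either 68 operations or a d of about 1.23 would be needed.

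This assumes two-sided alpha 0.05, one value per operation and independent operations. That 0.8 was typed in as f² is a plausible explanation but is not needed for the conclusion. This must be corrected, because it is the sole stated basis for the sample size.

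**What to change.** In Sample size determination:

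1. State the f², u and v that were entered, and the unit counted as N.
2. Reconcile f² with d, giving the d that the entered f² corresponds to (f² = d²/4 for equal groups).
3. Withdraw the claim of 0.90 power at d = 0.8.
4. Report the power of the RALS–LS contrast: about 56% at d = 0.8, or 90% at d of about 1.23, for 30 operations with one value each, treated as independent.
5. Say which SD d refers to. If averaging of repeated readings is relied on, state the correlation assumed.
6. Add that clustering of operations within 9 surgeons is not allowed for in this figure.

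The cost is wording only, with no further operations and no change to the analysis. The drawback is a less favourable stated power.

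### The power of 0.90 at N = 30 assumes independent observations, but the 30 units appear to be operations by nine surgeons whom the analysis itself models as a random effect, so the figure is not supported

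*Protocol*

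**What the plan says.** Under Sample size determination, the method is given as "Sample size was calculated in R Studio using the 'pwr' package and the 'pwr.f2.test' function". The inputs are up to ten predictors, a Cohen's d of 0.8 and alpha 0.05, and with "a desired statistical power of 0.90, this resulted in a sample size of 30", split 15 and 15. The target is named: "This was calculated for the right-sided muscle activation in RS compared to LS". The paragraph mentions no clustering, ICC or design effect, and does not say what n counts.

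Under Group characteristics, nine surgeons took part and one of them was in both groups, "meaning that the RALS group consisted of n=3 and LS group consisted of n=7". Under Distribution of Procedures, the text lists 14 robot-assisted and 16 laparoscopic operations. The last paragraph of Statistical Analysis fits a linear mixed model with "surgeon code as a random effect".

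**The concern.** A power function for an ordinary linear model treats every observation as independent. Thirty operations by nine surgeons are not independent if surgeons differ in their typical muscle activation, and the random effect in the analysis is there because they are expected to. The sample size therefore assumes something that the analysis section sets aside.

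The stake is how a large p value for RALS v LS will be read. The protocol says that p values are reported exactly and not dichotomously. Yet its own text already treats large p values as absence of difference: for METs per week (7800 v 3445, p = 0.137) and for predicted surgery length (p = 0.947). Carried over to the EMG comparison and backed by a power of 0.90, that habit would make an uninformative result look like evidence of no difference.

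**Working it through.** **Inputs from the protocol**
- N = 30 (15 + 15), power 0.90, alpha 0.05, ten predictors, d = 0.8 (Sample size determination).
- RALS operations: 4 + 1 + 2 + 3 + 3 + 1 = 14. LS operations: 5 + 3 + 4 + 1 + 1 + 1 + 1 = 16. Total 30 (Distribution of Procedures).
- Surgeons: 3 RALS, 7 LS, 1 in both, 9 in all (Group characteristics). That is 14/3 = 4.7 operations per RALS surgeon and 16/7 = 2.3 per LS surgeon.

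**Inputs assumed**
- ICC: not given; range 0.1 to 0.5.
- Operations per surgeon: not given; even spread taken as RALS 5/5/4 and LS 3/3/2/2/2/2/2, with the first surgeon of each list being the shared one.
- One value per operation; two-sided test.

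**Step 1. Reproduce the plan's figure under independence.** The function uses a noncentral F with noncentrality f² × (u + v + 1), where u is the number of predictors and N = u + v + 1.

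| Reading of the inputs | N for 0.90 | Power at N = 30 |
|---|---|---|
| u = 10, 0.8 entered as f² | 36 | 0.78 |
| u = 10, d converted: f² = 0.8²/4 = 0.16 | 138 | 0.18 |
| Two-group comparison, d = 0.8 | 66 (33 per group, normal approximation) | 0.56 (t) |

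None of these gives 30. So 0.90 is not obtained even before clustering is considered.

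**Step 2. Isolate the clustering.** To separate this from the effect-size question, take the effect that does give 0.90 for 15 v 15 independent operations. From the noncentral t with 28 df this is d = 1.23. It is a scaling device and not a protocol value.

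**Step 3. Simple design effect.** With m = 30/9 = 3.33 operations per surgeon, DE = 1 + (m − 1) × ICC, and power = Φ((1.960 + 1.282)/√DE − 1.960).

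| ICC | DE | Effective N = 30/DE | Power |
|---|---|---|---|
| 0.1 | 1.233 | 24.3 | 0.83 |
| 0.3 | 1.700 | 17.6 | 0.70 |
| 0.5 | 2.167 | 13.8 | 0.60 |

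This ignores the information from the surgeon who worked in both groups.

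**Step 4. Generalised least squares with the shared surgeon.** Compute the variance of the RALS − LS effect for the 30 operations under each covariance structure, and compare it with 1/14 + 1/16 = 0.134 for independent operations. Effective N = 30 × 0.134/variance. Power is at d = 1.23 with 28 df.

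| ICC | Random intercept only: effective N, power | All surgeon variance technique-specific: effective N, power |
|---|---|---|
| 0.1 | 26.4, 0.86 | 23.8, 0.82 |
| 0.3 | 23.7, 0.82 | 16.9, 0.68 |
| 0.5 | 25.2, 0.84 | 13.1, 0.57 |

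For example, at ICC 0.3 the variance is 0.170 in the first case (0.134/0.170 × 30 = 23.7 before and after rounding) and 0.238 in the second (16.9). In the technique-specific case, 8 df (ten surgeon-technique cells minus two) lowers the three powers to 0.74, 0.60 and 0.50.

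**Step 5. Look for cases where 0.90 survives.** Under the random-intercept model only:
- Even spread, ICC 0.7: effective N 33, power 0.93.
- Split 6/4/4 and 6/2/2/2/2/1/1 with the shared surgeon doing six in each group, ICC 0.5: effective N 33, power 0.93.
- Split 10/2/2 and 7/3/2/1/1/1/1 with the shared surgeon doing the most, ICC 0.3: effective N 33. If half the surgeon variance is technique-specific, the same split falls to an effective N of 18.

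**The case against.** Four arguments on the other side carry weight.

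First, a reader might infer that 30 operations by nine surgeons cannot reach 0.90. The documents do not support that. They give neither the ICC nor the operations per surgeon, and under the stated random-intercept model the shared surgeon provides a within-surgeon contrast. Step 5 shows that power can exceed 0.90 if the ICC is high or that surgeon did many operations in both groups, without doing most of them. What stands is that nothing in the protocol shows either condition.

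Second, the lowest powers (0.57, or 0.50 with 8 df) need surgeon-by-technique variance, which the protocol's model does not include. They are a sensitivity case. Under the stated structure, with an even spread, the loss is modest. The 8 df should not be carried over to the random-intercept case, where it is pessimistic.

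Third, the 0.90 was never obtained from the stated inputs, so the clustering loss is measured from a baseline that the protocol does not reach. If 0.8 is read as a single-predictor f², then d = 2√0.8 = 1.79, and power stays at 0.94 or above (28 df) for ICC 0.1 to 0.3 even under arm-specific design effects. But that reading contradicts the stated d of 0.8. The point that both defects must be fixed together is right.

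Fourth, the unit of n is inferred. A reader might conclude that 15 surgeons per group were intended and recruitment missed by two thirds. The listed operations sum to exactly 30, which makes operations the more likely unit, so the text gives no firm ground for claiming a shortfall.

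**Conclusion.** The concern holds in this form: the stated 0.90 is unsupported, because it comes from an independent-observation calculation while the protocol's own design and model describe operations grouped within nine surgeons. This is an inconsistency between the sample-size rationale and the analysis. The planned mixed model does allow for surgeon, so the criticism is of the power claim and not of that random effect.

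The size is conditional. With the effect scaled to 0.90 at 15 v 15 independent operations, an even spread over surgeons, ICC 0.1 to 0.5 and 28 df, power is about 0.82 to 0.86 under the stated model. It runs from about 0.82 down to 0.57 if all surgeon variance is technique-specific. Values of 0.90 or more are possible under the stated model but not demonstrated. Clustering is also not the only cause, and perhaps not the largest: with ten predictors and 0.8 entered as f², power at N = 30 is 0.78 under independence.

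**What to change.** Rewrite the Sample size determination paragraph so that it:
1. states that n counts operations, and reports operations per surgeon in each group, including the shared surgeon;
2. settles the effect-size input, since d = 0.8 is quoted with a function that takes f²;
3. replaces the 0.90 with the power, or the detectable difference, for 14 RALS operations from 3 surgeons and 16 LS operations from 7 (1 shared), under the random-intercept model over a stated ICC range such as 0.1 to 0.5, with the degrees of freedom named;
4. gives surgeon-by-technique variance as a sensitivity case.

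Items 2 and 3 must be done together, because no power can be restated until the effect size is fixed. Add a sentence that a large p value for RALS v LS is not evidence of no difference.

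The cost is one paragraph and a short calculation or simulation. No new participants or data are needed. The drawback is that the stated power will probably be less favourable.
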